1. LIST OF ABBREVIATIONS AND ACRONYMS

Term/Abbreviation	Definition
ANC	Absolute Neutrophil Count
ARDS	Acute Respiratory Distress Syndrome
CMV	Cytomegalovirus
COMS	Core Outcome Measurement Set
ELISA	Enzyme-Linked Immunosorbent Assay
ETA	Endotracheal Aspirate
GCSF	Granulocyte-Colony Stimulating Factor
GRAIL	Ganciclovir/Valganciclovir for Prevention of CMV Reactivation in Acute Injury of the Lung and Respiratory Failure
HCT	Hematopoietic Cell Transplant
ICU	Intensive Care Unit
IG	Immunoglobulin
IL	Interleukin
ITT	Intent-To-Treat
LFA	Lateral Flow Assay
NPV	Negative Predictive Value
PEEP	Positive End Expiratory Pressure
PPV	Positive Predictive Value
RCT	Randomized Controlled Trial
RSFD	Respiratory-Support-Free Days
SBT	Spontaneous Breathing Trial
SOFA	Sequential Organ Failure Assessment
SOT	Solid Organ Transplant
VFD	Ventilator-Free Days
WBC	White Blood Cell
MNAR	Missing Not at Random
GCV	Ganciclovir

2. INTRODUCTION

The purpose of this Statistical Analysis Plan (SAP) is to provide a description of the statistical analyses that will be conducted for the GRAIL3 final study reports.

2.1 General Design Considerations

The following is a summary of the protocol.

Short Title: A Phase 3 Study of Ganciclovir Use in Patients with Acute Respiratory Failure and Sepsis

Funder: NHLBI

Protocol Team: [name], PhD
 [name]
 [name]
 [name], MSc

Sample Size: Approximately 500 participants

Study Population: Immunocompetent, CMV seropositive adults hospitalized with sepsis and acute respiratory failure requiring respiratory support

Study Sites: Sites selected by the GRAIL Executive Committee

Study Hypotheses: We hypothesize that IV ganciclovir administered early in critical illness will effectively suppress CMV reactivation in CMV seropositive adults with sepsis-associated acute respiratory failure, thereby reducing lung damage and accelerating recovery from respiratory failure by direct and indirect mechanisms, and leading to improved clinical outcomes.

Study Design: Multicenter randomized placebo-controlled double-blind trial, [randomized in blocks for balance across study sites, with interim analyses of safety].

Study Duration: 180 days per patient

Study Product: Ganciclovir sodium: 2-amino-9-76,9-dihydro-3H-purin-6-one.
 Placebo for ganciclovir: [normal saline].

Study Regimen: 500 adults will be randomized in a 1:1 ratio to receive either the study drug or placebo. Participants randomized to intervention will use IV ganciclovir only. Participants will receive ganciclovir or normal saline twice daily from day 1 through day 5 and once a day from day 6 through day 28, hospital discharge, death, whichever occurs earlier.

		Schedule of administration*	
		Day 1 through Day 5	Day 6 through Day 28 or hospital discharge, whichever occurs earlier
Arm	N	Twice daily	Once daily
1	250	Ganciclovir 5 mg/kg intravenously	Ganciclovir 5 mg/kg intravenously
2	250	Normal saline intravenously	Normal saline intravenously
Total	500		

* "Day" on this table refers to study day. Day 1 is the first day of study drug administration.

2.2 Study Objectives and Endpoints

Primary Objective: To evaluate whether administration of ganciclovir increases respiratory-support-free days (RSFDs) in immunocompetent patients with sepsis-associated acute respiratory failure.

Primary Endpoint: RSFDs will use a “last off” approach (detailed in Protocol V5 Section 6.1.1), meaning that RSFDs will be counted when a participant gets off and stays off of respiratory support (as defined in Protocol V5 Section 4.1.1) to day 28. Participants who do not survive through day 28 are assigned zero RSFDs.

Secondary Objectives:

1. To evaluate whether administration of ganciclovir increases VFDs in immunocompetent patients with sepsis-associated acute respiratory failure.
2. To evaluate whether administration of ganciclovir increases total RSFDs (all RSFDs, instead of last-off approach) in immunocompetent patients with sepsis-associated acute respiratory failure.
3. To evaluate whether mortality and time to death in the 28 and 180 days is different among ganciclovir recipients relative to placebo recipients, respectively.
4. To evaluate whether duration of mechanical ventilation among survivors in the first 28 days is different among ganciclovir recipients relative to placebo recipients.
5. To evaluate whether duration of respiratory support among survivors in the first 28 days is different among ganciclovir recipients relative to placebo recipients.
6. To evaluate whether oxygenation is different among ganciclovir recipients relative to placebo recipients.
7. To evaluate whether ICU-free days in the first 28 days are different among ganciclovir recipients relative to placebo recipients.
8. To evaluate whether CMV DNA detection in plasma and endotracheal aspirate (ETA) by day 28 is different among ganciclovir recipients relative to placebo recipients.
9. To assess the number and severity of reportable adverse events and reportable serious adverse events in the first 28 days in both groups.

Secondary Outcomes:

1. VFDs (defined to be 28 days minus the duration of mechanical ventilation through day 28 since randomization [a key secondary endpoint]). Participants who do not survive through day 28 are assigned zero VFDs.
2. Total RSFDs (calculated as 28 days minus each day of respiratory support through day 28 since randomization). Participants who do not survive through day 28 are assigned zero respiratory-support-free ventilator-free days.
3. Mortality by day 180 (day 28, day 180, time-to-event).
4. Duration of mechanical ventilation (among survivors) by day 28.
5. Duration of respiratory support (among survivors) by day 28.
6. Oxygenation ($\text{PaO}_2/\text{FiO}_2$ ratio) daily on study days 1–7.
7. ICU-free days by day 28.
8. CMV DNA detection in plasma and endotracheal aspirate (ETA) by day 28 (>0 IU/mL, >1000 IU/mL).
9. Number of patients with reportable adverse events of Grade 3 or higher by day 28.

Exploratory Objectives:

1. To evaluate whether static respiratory system compliance at randomization, day 4, and day 7 differs between ganciclovir recipients and placebo recipients.
2. To assess the occurrence of invasive bacterial and fungal infections in ganciclovir recipients compared to placebo recipients.
3. To evaluate whether organ dysfunction scores (regular SOFA variables, including respiratory, coagulation, liver, cardiovascular, CNS, and renal function, with the Sat/FiO_2 ratio replacing the

PaO₂/FiO₂ ratio used in the standard SOFA score) differ between ganciclovir recipients and placebo recipients.

4. To assess long-term life quality as measured by the Acute Respiratory Failure Core Outcome Measurement Set (COMS), which will include the Katz Index of Independence in Activities of Daily Living (ADL) and Lawton – Brody Instrumental Activities of Daily Living Scale (IADL) completed by legally authorized representatives (LARs) or participants at baseline; and the ADL, IADL, Hospital Anxiety and Depression Scale (HADS), EQ-5D-5L, and Impact of Events Scale – Revised (IES-R), completed by patients at day 180.
5. To assess risk factors associated with CMV reactivation kinetics, including demographics, comorbidities, severity of illness, organ dysfunction, lymphocyte count, time from hospital admission to enrollment, ventilation type, viral load prior to randomization, and duration of illness before hospital admission.
6. To characterize the relationship between CMV viral load kinetics in blood and lung compartments and respiratory-support-free days (RSFDs), ventilator-free days (VFDs), and secondary clinical outcomes, including oxygenation, static respiratory system compliance, mortality, and duration of mechanical ventilation in survivors.
7. To assess the performance of a rapid lateral flow CMV serostatus assay compared to clinically performed assays for CMV IgG antibodies, as conducted in CLIA-approved laboratories, throughout the study and at trial completion.
8. To evaluate assays characterizing immunity to CMV, including cellular immunity, neutralizing antibodies, antibody epitope expansion, and transcriptional signatures.
9. To determine whether the use and duration of ECMO differ between ganciclovir recipients and placebo recipients.
10. To assess the occurrence of neuromuscular blockade in ganciclovir recipients compared to placebo recipients.
11. To assess the use of prone positioning in ganciclovir recipients compared to placebo recipients.

Exploratory Endpoints:

1. Static respiratory system compliance at randomization, day 4 and day 7.
2. Invasive bacterial and fungal infections.
3. Organ dysfunction scores (regular SOFA variables including respiratory, coagulation, liver, cardiovascular, CNS and renal; as well as SpO₂/FiO₂ ratio).
4. The NHLBI-endorsed Acute Respiratory Failure Core Outcome Measurement Set (COMS) in survivors at day 180.
5. Risk factors for CMV reactivation (>0 IU/mL, >1000 IU/mL) in plasma and lung:
 - 1) Sex, age, race
 - 2) Co-morbidity
 - 3) APACHE III score
 - 4) SOFA score and individual components
 - 5) Lymphocyte count
 - 6) Time from hospital admission
 - 7) Viral load prior to randomization
6. Relationship of CMV viral load with RSFDs and VFDs and secondary clinical outcomes:
 - 1) Viral load: initial (baseline), peak, slope, area under the curve (AUC).
 - 2) Association with RSFD and VFD, day-28 mortality, duration of mechanical ventilation in survivors, static compliance, PaO₂/FiO₂.
 - 3) Baseline viral load in plasma and lung
7. Viral load kinetics among survivors in day 7 and 14.
8. Sensitivity, specificity, PPV and NPV of rapid lateral flow CMV serostatus assay.
9. CMV cellular immunity, neutralizing antibodies, antibody epitope expansion, and transcriptional signatures.
10. Use of ECMO at any time during the post-randomization period, and duration if used
11. Occurrence of neuromuscular blockade.

12. Prone positioning status.

2.3 Randomization

Patients who met all inclusion and exclusion criteria were randomized to receive standard ICU care (including lung-protective ventilation and weaning protocols, if mechanically ventilated) plus either the intervention or placebo. Randomization was stratified by site and implemented using block randomization lists created by SCHARP. Assignment was conducted through the Medidata RTSM system.

2.4 Blinding

Participants and site staff (except site pharmacists) were blinded to treatment assignments. Study drug allocation was accessible only to site pharmacists, contract monitors (or the central site IDS pharmacist as backup), and unblinded statisticians responsible for trial oversight. Randomization assignment data were restricted to unblinded statisticians. Emergency unblinding was available 24/7 via Medidata RTSM. Communication regarding treatment allocation between clinical and pharmacy staff was strictly prohibited. DSMB members were unblinded to treatment assignment to permit ongoing safety monitoring, and closed DSMB reports included treatment group information.

2.5 Sample Size and Power

To estimate the required sample size for this study, we used ventilator-free days (VFD) data from the GRAIL Phase 2 trial and available literature on RSFDs, assuming similar variance. A clinically meaningful difference in RSFDs between treatment arms was assumed to be 2.74 days, with an empirically estimated standard deviation of 9.4 days. To detect this difference with 85% power using a two-sided test at a 5% significance level, a total sample size of 426 participants (213 per group) was required for the primary analysis.

To account for feasibility and potential dropout—including 1% lost to follow-up and 2% early discontinuation due to negative CMV ELISA results—the final sample size was increased to 500 participants. A pre-specified sample size re-estimation was conducted after 50% of participants had reached the primary endpoint; based on the observed data, the original sample size was retained.

Mortality was included as a secondary endpoint. Assuming a 20% mortality rate in the control arm, the final sample size of 500 provides 80% power to detect a hazard ratio of 0.52 between the Ganciclovir and placebo groups.

3. GENERAL DATA ANALYSIS CONSIDERATION

3.1 Analysis Set(s)

The **Intent-to-Treat (ITT) Analysis Set** will include all enrolled and randomized participants. However, one exception applies: participants who are withdrawn from the study before receiving any dose of the study drug will not undergo study procedures and will be excluded from the ITT analysis. Participants who are withdrawn after receiving at least one dose will continue to receive safety assessments (e.g., creatinine and complete blood count with differential) for up to 48 hours. Although no study bio-samples will be collected after withdrawal, clinical data available in the medical record (e.g., respiratory-support-free days) will continue to be collected per protocol, and such participants will be included in the ITT analysis. **The ITT set will serve as the primary analysis population.**

Two modified Intent-to-Treat (mITT) Analysis Sets will also be defined:

The first mITT set will exclude participants who are withdrawn from the study for any reason after receiving at least one dose of study drug. Reasons for withdrawal may include, but are not limited to: participant withdrawal of consent, inability or unwillingness to comply with study procedures, refusal to continue participation by the participant or their legally authorized representative (LAR), or an initial positive CMV LFA test followed by a confirmatory negative CMV ELISA result.

The second mITT set will include only those participants who survive and are followed through day 28.

In addition, a **classical ITT set**, which includes all randomized participants regardless of treatment receipt or study completion, will be retained for completeness.

3.2 Statistical Analysis Issues

Every effort will be made by the Data Coordinating Center (DCC) to ensure complete, accurate, and high-quality data collection and annotation. However, as with all clinical trials, challenges are anticipated. Given the high mortality rate in this population, missing data is a key issue that may affect both primary and secondary endpoints (e.g., CMV reactivation [missing viral load values], organ dysfunction, and outcomes from the NHLBI-endorsed acute respiratory failure core measurement set). This section outlines the anticipated sources of missing data and corresponding mitigation strategies, informed by experience from the GRAIL Phase 2 trial.

Missing Data in Primary Outcome

Missingness in the primary outcome, RSFDs, is expected to be minimal (~2%) and is likely to be missing not at random (MNAR), primarily due to participant withdrawal of consent. Such withdrawals typically occur in more severely ill participants under high stress. Given the low expected frequency, missing data in RSFDs will be excluded from the primary analysis without imputation.

Missing Data in Some Secondary/Exploratory Outcomes Due to Study Design

Some secondary endpoints (e.g., static respiratory compliance) may be unavailable due to early extubation, ICU discharge, or death prior to scheduled biospecimen collection. For instance, if ganciclovir reduces respiratory support duration, extubated participants may not be eligible for endotracheal aspirates, potentially biasing the analysis. To minimize missingness, biospecimen collection was scheduled at Day 7 (± 1 day), when approximately 40% of participants are expected to remain alive and intubated. If missing data persist despite this timing, we will apply imputation techniques such as last observation carried forward (LOCF), multiple imputation (MI), or conduct sensitivity analyses. If missingness remains substantial, limitations will be acknowledged in interpreting results.

Missing Data in Covariates

Missing covariate data may result from death, withdrawal, or other causes. If covariate missingness exceeds 5%, it will be addressed analytically. Covariate missingness is expected to be MAR, and will be handled using either inverse probability weighting (IPW) or multiple imputation (MI) [1, 2].

- Weighting Adjustments:
 - Estimate the probability of missingness using logistic regression with baseline covariates as predictors.
 - Calculate IPW as the reciprocal of predicted probabilities.
 - Apply weighted generalized estimating equations (WGEE) or weighted regression models to reduce bias in treatment effect estimates.
- Multiple Imputation (MI):
 - Use Multivariate Imputation by Chained Equations (MICE) to impute missing covariates.
 - Perform 20–50 imputations to ensure stability.
 - Combine estimates across imputations using Rubin's rules to derive valid statistical inference.

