In the GRAIL Phase 2 trial, VFDs difference was estimated to be 2.74 days. As shown in Table 6-2, to detect a similar difference (of 2.74 days) in RSFDs between the two arms with 85% statistical power, a sample size of 426 subjects ($213 \times 2 = 426$) total is required in this Phase 3 trial's primary analysis, and that is what we power for in this study. Findings from previous RCTs suggest that approximately 12% of subjects in this Phase 3 RCT will be CMV PCR positive at baseline when rapid lateral flow assay is used to assess serostatus. This 12% estimate is lower than the proportion reported in the GRAIL Phase 2 study due to the use of the rapid lateral flow assay, which we estimate will shorten the time to randomization from ICU admission by approximately 1 day and reduce the baseline PCR positivity rate. Furthermore, we anticipate that the percentage of subjects who are PCR positive at baseline will be lower among individuals on respiratory support (as defined in Section 4.1.1) compared with individuals on mechanical ventilation alone (as in the GRAIL Phase 2 trial) because we will be capturing some eligible participants earlier in the course of their respiratory failure when less time has elapsed to allow for CMV reactivation (both because we will allow enrollment of patients on NIV and HFNC oxygen and because time to obtain consent from participants able to consent for themselves may be shorter than consent through LARs. Since the population for primary analysis includes all patients without regard to PCR positivity at baseline, we inflate the sample size by a factor to

account for the power loss by including these cases in our primary analysis population. We also assume a dropout rate of 1% lost to follow-up for the primary endpoint, based on findings from other large ICU trials, and a dropout rate of 2% for early discontinuation following a negative CLIA CMV ELISA test among randomized participants who have received at least one dose of study drug. Accounting for both of these effects, the sample size for GRAIL Phase 3 trial was increased to 500 subjects in total.

6.1.2 Power Calculations for Secondary Endpoints.

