The absence of data pertaining to some secondary endpoints (for example, static respiratory system compliance) may be problematic if participants are discharged from the ICU, are on pressure support after being extubated, or expire prior to our pre-specified time points for endotracheal aspirates and serum collection. For example, if the Ganciclovir intervention reduces duration of respiratory support, it may bias the results because participants cannot undergo endotracheal aspirate if they are extubated. Thus, to minimize missing data and to maximize the CMV detection rate, we have selected multiple time points for the endotracheal aspirate (Day 1 and twice weekly until Day 28). If these issues still occur, we will address them in the analysis phase using data imputation methods, or by acknowledging it as a limitation of any analyses conducted with these variables.

6.4.1.3 Missing Data in covariates.

Missing data can occur in covariates as well, due to factors such as death, withdrawal, or other reasons; this will need to be accounted for in our analyses, if overall missingness (in covariates) increases beyond 5%. Since we expect covariate missingness in this study to be MAR (missing at random), we will use weighting adjustments (for example, weighted generalized estimating equations) or multiple imputation methods [98, 99] to deal with covariate missingness.

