APPENDIX A: TIME AND EVENTS SCHEDULE

Visit	Screening	01	02	03	04	05	06	07	08	09	10	Assay Location
Day	-4 to 1	1	4	7	11	14	18	21	25	28	180	
Window (+/- days)	0	1	1	1	1	1	1	1	1	4	42	
Informed consent	X	-	-	-	-	-	-	-	-	-	-	
Administer Study Drug		Patient receives 5 days of ganciclovir (or placebo) intravenously TWICE daily, then up to 23 additional days of ganciclovir (or placebo) intravenously ONCE daily in hospitalized patients.										
Blood collection (ml) vol. estimated:												
Pregnancy testing	3 ^a			3 ^b								L
CMV Serology	3	-	-	-	-	-	-	-	-	-	-	L/A
Genomic analysis sample ^c	-	5	-	-	-	-	-	-	-	-	-	S
T cell immunity samples ^{c,e,m}	-	(30)	-	-	-	-	-	-	-	-	-	S
Serum Creatinine ^{d,n}	1	1	1	1	1	1	1	1	1	1	-	L
CMV PCR (plasma) ^{d,c}	-	5	(5)	5	(5)	5	(5)	5	(5)	5	-	S
CBC, w/diff, platelets ^d	1	3	3	3	3	3	3	3	3	3	-	L
Blood volume (estimate)	8	14 (44)	4 (9)	9	4 (9)	9	4 (9)	9	4 (9)	9	-	
Endotracheal aspirate (ETA)												
CMV PCR ^{e, f}	-	X	(X)	(X)	(X)	(X)	(X)	(X)	(X)	(X)	-	S
Clinical Assessments:												
SOFA ^g and, fluid balance		Daily on Days 1-7			X	X	X	X	X	X		
Ventilator (including static compliance), ^f NIV, HFNC parameters, and FiO ₂		Daily										
Antiviral, antibacterial or antifungal medications ^h		Daily on Days 1-7			X	X	X	X	X	X		
Apache III		X										
AE/SAE monitoring		X	X	X	X	X	X	X	X	X		
ECMO, prone positioning, steroids, immunosuppressive medications, and neuromuscular blockers		X	At any time while on study; collected at discharge									
Vital status			ICU and hospital mortality collected at discharge									X
Bacteremia, fungemia, nosocomial pneumonia (including ventilator-associated pneumonia)			At any time while on study; collected at discharge									
Contact (e.g. phone)										X ⁱ	X ^k	
NHLBI COMS survey		X ^l									X ^l	

L = local test; S=Seattle, WA; A= ARUP in Utah

^a Pregnancy tests (serum or urine) performed within 120 hours before enrollment are acceptable.

^b At day 7 or discharge, whichever is earlier (if day 7 is missed, at discharge is acceptable). Only serum test is acceptable.

- c All samples will be stored for analysis at the end of the study
- d All blood draws will occur only during hospitalization, blood chemistry, CBC and platelet values can be obtained from clinical testing result if available, thereby reducing required blood volume
- e Time points in () only in patients with intensified monitoring (n=150).
- f Can only be collected if subject is ventilated
- g While in the ICU

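### SAP 3.2 leaves last observation carried forward open for static compliance and quantitative airway viral load after extubation, ICU discharge or death, when about 60% of participants are expected to have no Day-7 intubated value

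*SAP*

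**What the plan says.** SAP 3.2, under missing secondary and exploratory outcomes, uses static compliance as its example. It says values "may be unavailable due to early extubation, ICU discharge, or death prior to scheduled biospecimen collection". It adds that if ganciclovir shortens respiratory support, extubated patients cannot give aspirates and the analysis may be biased. It places collection at Day 7, "when approximately 40% of participants are expected to remain alive and intubated". For data still missing, "we will apply imputation techniques such as last observation carried forward (LOCF), multiple imputation (MI), or conduct sensitivity analyses". If missingness is substantial, limitations will be acknowledged.

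Protocol 6.4.1.2 covers the same problem without naming a method: "we will address them in the analysis phase using data imputation methods, or by acknowledging it as a limitation". LOCF therefore enters only through the SAP.

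Three other places set the scope:

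- **Appendix A**, note f, attached to both the ETA and the ventilator/compliance rows: "Can only be collected if subject is ventilated". Protocol 9.6 (baseline ETA) and 9.11 (compliance) agree.
- **SAP section 10, item 8** analyses CMV DNA detection by cumulative incidence and Gray's test, with death as a competing risk. It names no LOCF.
- **Protocol 6.2.2** plans a mediation analysis with static compliance as mediator, to judge whether any ganciclovir effect runs through the lung. SAP 2.2 lists viral load peak, slope and area under the curve as exploratory measures.

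**The concern.** A value missed while the patient is still ventilated is a missing observation, and imputing it is reasonable. After extubation or death there is no compliance or tracheal aspirate left to measure. Carrying a value forward then holds a recovered patient at a ventilated reading and a dead patient at a pre-death reading, and analyses both as Day-7 data.

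The harm comes from the link with treatment. The trial's hypothesis is that ganciclovir speeds recovery from respiratory failure. If it changes time to extubation or death, the arms carry forward different shares of earlier values. Where compliance or viral load drifts over time, that alone separates the arm means. LOCF also flattens individual viral-load slopes and distorts areas under the curve.

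At stake are the Day-4 and Day-7 compliance comparisons, the mediation analysis, and the quantitative ETA viral-load summaries. These are the analyses likely to be used to explain the trial's result.

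**Working it through.** **Inputs from the documents**

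- Alive and intubated at Day 7: about 0.40 (SAP 3.2).
- Planned total: 500.
- Patients not intubated at entry are enrolled: "we will allow enrollment of patients on NIV and HFNC oxygen" (protocol 6.1.1). The share ever intubated is not given.
- Post-baseline ETA is planned only in the intensified-monitoring subset, n=150 (Appendix A, note e).
- Phase 2 sepsis cohort, ventilation duration, median (IQR): placebo 6 (3-11) days, n=66; ganciclovir 5 (3-8) days, n=71 (protocol Table 2-1).

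**Step 1. Is the 40% plausible?** The SAP gives no derivation, so it cannot be reproduced. Linear interpolation between the Phase 2 median and upper quartile gives the share ventilated beyond 7 days:

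- Placebo: 0.5 - 0.25 × (7-6)/(11-6) = 0.45
- Ganciclovir: 0.5 - 0.25 × (7-5)/(8-5) = 0.33
- Weighted: (66 × 0.45 + 71 × 0.333)/137 = 0.39

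This is close to 40%, but Phase 2 patients were all mechanically ventilated. If the 40% came from there, which the SAP does not say, it describes patients intubated at entry rather than all participants.

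**Step 2. Share with no Day-7 value.** 1 - 0.40 = 0.60, or 0.60 × 500 = 300 participants, from extubation, ICU discharge, death or never having been intubated.

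**Step 3. Share of analysed Day-7 compliance values that LOCF would supply.** Let p be the share of participants with any compliance value by Day 7 (assumed). Those with an earlier value but none at Day 7 number p - 0.40, so the carried share is (p - 0.40)/p.

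| p (assumed) | Carried share | No value at all |
|---|---|---|
| 1.0 | 60% | 0% |
| 0.9 | 56% | 10% |
| 0.8 | 50% | 20% |
| 0.7 | 43% | 30% |
| 0.6 | 33% | 40% |
| 0.5 | 20% | 50% |

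**Step 4. ETA viral load.** Within the 150 subset the same formula applies. If LOCF were instead applied in all 500 with Day-7 samples only from the subset, 0.40 × 150 = 60 would be observed. The carried share would be (500p - 60)/(500p): 88% at p=1.0, 85% at p=0.8, 80% at p=0.6. So 60% is not a firm figure for ETA.

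**Step 5. How a false difference arises.** Suppose both arms have the same underlying mean path, the mean changes by D between the last measurement and Day 7, and the carried shares are c1 (ganciclovir) and c0 (placebo). The LOCF contrast is then -(c1 - c0) × D, although the true contrast is zero. The documents give neither D nor c1 - c0 for this trial. As an illustration only, D = 5 mL/cmH2O with a gap of 10 to 15 points gives a shift of 0.5 to 0.75 mL/cmH2O. The Step 1 gap (0.45 - 0.33, about 12 points) lies in that range. With compliance rising and ganciclovir shortening ventilation, the shift counts against ganciclovir.

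**The case against.** The strongest reply is that little rests on this. Compliance is exploratory, SAP sections 8 to 10 specify no Day-7 compliance contrast, and SAP section 11 points to a companion plan for exploratory and post hoc analyses that may settle the method. SAP 3.2 offers LOCF only as one example beside MI or sensitivity analyses, and itself warns of bias from extubation. Compliance is recorded daily while ventilated, so a carried value may be recent and D small. For airway samples, the protocol also reduces gaps by design: "we have selected multiple time points for the endotracheal aspirate (Day 1 and twice weekly until Day 28".

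Much of this stands. It limits the reach of the point and prevents a firm bias estimate. It does not answer the point, because the text in force still allows LOCF past death or extubation and leaves the choice of method open.

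Four stronger readings are tempting and not supported:

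- **That about 60% of Day-7 values would be carried forward.** The SAP's figure gives the share without a Day-7 value. Never-intubated patients have nothing to carry, so for compliance 60% is a ceiling.
- **That LOCF shrinks the standard error by √0.40 = 0.63, so that a 95% interval covers 2Φ(1.96 × 0.63) - 1 = 78%.** This treats carried values as copies of other patients' data. Each is the patient's own measurement, and patients remain independent. In a simulation with 250 per arm, 60% carried forward at random and no arm difference, coverage was about 95% at Day 4 to Day 7 correlations of 0 and 0.6. The fault is bias and an ill-defined target, not this loss of coverage.
- **That the CMV DNA secondary endpoint is compromised.** Its analysis in SAP section 10 does not use LOCF.
- **That the SAP assumes missing at random for these outcomes.** It states that only for covariates.

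**Conclusion.** The point holds in a limited form. SAP 3.2 permits LOCF for compliance and quantitative ETA viral load missing through extubation, ICU discharge or death, and does not distinguish these from samples missed on the ventilator. Used that way, LOCF gives a contrast that can differ between arms with no true effect, and the same distortion would pass into the compliance mediation analysis.

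The affected fraction may be large: about 60% of participants lack a Day-7 intubated value, and carried values make up 33% to 60% of analysed compliance values if 60% to 100% were ever measured. That range rests on an assumed p and on the SAP's underived 40%. The size of the bias cannot be fixed from the documents, and the 0.5 to 0.75 mL/cmH2O above is illustrative. This should be corrected before the exploratory analyses are run, but it does not threaten the trial's main efficacy conclusions.

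**What to change.** In SAP 3.2:

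1. Delete LOCF.
2. State that compliance and ETA values are not imputed after extubation or death. Classify an ICU discharge by whether the patient was still invasively ventilated.
3. Limit MI to samples missed while the patient was still invasively ventilated.
4. Report the observed-only comparison as descriptive, with the numbers extubated, discharged from ICU and dead by arm at each time point, and the number ever measured.
5. Apply the same rules to compliance in the protocol 6.2.2 mediation analysis and to ETA viral-load summaries, and repeat them in the companion exploratory plan.

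A ranked outcome with death worst could be an optional sensitivity analysis. It is not needed for the correction, and it would overlap with the free-day endpoints.

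The cost is a few lines of SAP text and no new data. The downside is that the Day-7 comparison uses fewer values and is conditional on still being ventilated, so it is not a randomized comparison and must be labelled accordingly.
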